## II. Purpose and Background

The purpose of this study is to evaluate the safety and efficacy of an over-the-counter (OTC) intraoral mouthpiece to reduce snoring. A secondary objective is to evaluate the behavior of patients at high risk for sleep apnea to determine whether they will seek a conclusive diagnosis with a sleep study.

# Background

Snoring is a common condition which negatively affects the quality of sleep for both snorers and their partners. It is estimated that nearly 30% of men and 9% of women suffer from habitual snoring, with risk factors including obesity, age (>40), smoking, and alcohol consumption. (Kara CO et al, *The prevalence of snoring in the adult population*, Kulak Buran Bogaz Ihtis, 2005, 14(1-2), 18-24).

Poor sleep quality has been shown to be a health risk for many conditions, including heart disease and hypertension, obesity, diabetes, mood disorders, reduces immune response and many others (http://healthysleep.med.harvard.edu/healthy/matters/consequences/sleep-and-disease-risk)

Snoring is often caused by a narrowing of the airway. As air is forced through this narrow passage it vibrates the skin of the airway, causing the distinctive sound of snoring. It is well established that slight changes in the positioning of the mouth, teeth, or tongue can significantly affect snoring.

This study is evaluating the safety and efficacy of an intraoral mouthpiece to reduce snoring. A similar intraoral mouthpiece, Zyppah Boil and Bite, is prescribed on the internet to more than 100,000 people every year. It is cleared under K111680.

The mouthpiece tested in this clinical trial is being evaluated as an over-the-counter product. It has the same features, except it does not move the lower jaw forward. The mouthpiece is designed to change the position of the mouth, and thereby increase the capacity of the airway. It also has a silicon strap placed over the tongue to stabilize it and open the airway. The mouthpiece is placed in boiling water to soften the plastic and then inserted in the mouth, customizing the shape for each user.

One concern in providing an OTC intraoral mouthpiece is the belief that a device intended to reduce snoring cannot reduce snoring associated with obstructive sleep apnea (OSA) and may cause patients not to enroll in a sleep study to diagnose (OSA). However, it is estimated by the American Sleep Apnea Association that 80% of moderate and severe sleep apnea remains undiagnosed. Our theory is that most patients are not making appointments for sleep studies to diagnose their sleep apnea, but are willing to buy an OTC mouthpiece to improve their snoring.

## Obstructive Sleep Apnea (OSA)

Obstructive Sleep Apnea (OSA) is a sleep disorder where breathing stops and restarts multiple times during the night, interrupting sleep and often abruptly awakening the patient with a feeling of suffocation. There is significant overlap between snoring and patients with obstructive sleep apnea, which is estimated to affect 3-7% of men and 2-5% of women (Punjabi NM, *The Epidemiology of Adult Obstructive Sleep Apnea*, Proceedings of American Thoracic Society, 5:2, 2008).

The vast majority of those with sleep apnea also habitually snore, though the majority of habitual snorers *do not* have sleep apnea. From prevalence estimates, approximately 10% of male and 22% of female snorers may also have OSA. Women are eight times more likely to have their OSA undiagnosed than men.

The instructions for use of the mouthpiece helps the patient assess their risk of mild, moderate or severe OSA and may encourage them to register for an inexpensive home sleep study. It is hoped that this device may help some habitual snorers identify their risk of OSA and seek treatment. This clinical trial will also monitor the behavior of these users, looking to see whether they i) seek a sleep study, ii) return the device for a refund or iii) decide to use the snoring device. In the first two cases, they will be dropped from the clinical trial.

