#### Study Design

Patients will enroll in the study online. The on-line experience has been carefully designed to mimic the experience of buying the device in a retail store or on a website without consulting a sleep professional or dentist. After filling out a short online questionnaire to determine their initial symptoms and signing the informed consent, the product and instructions will be shipped to them. The device is used for a period of 10 days in the clinical trial. An email prompting them to complete a follow-up questionnaire will be sent ten days after the device has been received. Upon completion of the follow-up survey, the cost of the device will be refunded to the patient, incentivizing completion of the study.

The surveys will ask the patients to qualitatively and quantitatively compare their snoring before use of the device and after 10 days of using the device.

As part of the follow-up survey, users will be asked if they self-identified (on the basis of the product instructions) as being at risk for OSA. If they answer positively, they will be asked about their response, including whether they sought medical care, enrolled in a sleep study, or discontinued use of the device.

A two-sample t-test will be used to analyze the change from the initial survey to the follow-up survey, with patients serving as their own controls.

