## Methods and Procedures

## Methods and Procedures

Subjects who are interested in reducing their snoring will be recruited online. In order to participate in the trial, they will complete a pre-trial questionnaire, as well as review and sign the Informed Consent.

Assuming they satisfy the Inclusion and Exclusion criteria and sign the Informed Consent (includes the inclusion/exclusion criteria), they will purchase the device for \$90. The intraoral device and patient instructions will be mailed to them (Attachment E).

Once the subject is able to participate in the study, the device is placed in boiling water to soften it. While still warm, the device is placed in the mouth and molded to the individual patient. This is the same procedure used with many intraoral mouthpieces and devices including the Zyppah Boil and Bite.

The subject will be asked to use the intraoral device each night for ten consecutive nights. After they have used the device for ten days, a follow-up survey will be emailed to the subject. The patient will respond to the questions in the survey. After they have completed the follow-up survey and returned it, the subject will receive a full refund for the cost of the device (\$90). This is intended to increase compliance with the protocol.

This study will also evaluate the response of subjects who are at high risk of obstructive sleep apnea. The product instructions will contain a brief questionnaire (Attachment D, STOP-BANG Survey) assessing the subject's risk for OSA. If they are determined to be high-risk by the self-administered questionnaire, they will be given the following options: 1) complete a full, overnight in-office sleep study, 2) complete a discounted in-home sleep study, or 3) discontinue use of the device and return it for a full refund. The response of these subjects will be monitored to see how they respond and whether they continue to use the device or seek medical attention to evaluate their risk of sleep apnea.

This is a non-significant risk study, and the only 'extra' requirements for this study are the completion of the pre-study and post-study questionnaires by the patient.

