# Data Collection

- Attachment A is the list of questions to gather personal information about the subject, including age, gender, weight, height and contact information. This will allow for the calculation of Body Mass Index (BMI), a well-known risk factor in both snoring and obstructive sleep apnea. This attachment also contains the Inclusion/Exclusion criteria, where potential subjects will be asked to review and certify that they meet the requirements of the trial (they will also see this information later in the process at the Informed Consent).
- Attachment B is the Visual-Analog Scale (VAS) asking potential subjects how much their snoring is bothering them and their partner (if applicable). The VAS method is commonly used and has been validated for patient satisfaction (Brokelman et al, 2012).
- Attachment C is the Snoring Severity Scale (SSS). This validated, three-question survey has been shown to accurately assess the severity of snoring and the risk for obstructive sleep apnea (Morris L et al, 2008)
- Attachment D is the Stop-Bang Assessment, which is the most frequent assessment used to determine the risk of sleep apnea. This 8-question survey has been validated as a risk assessment for moderate to severe sleep apnea (Nagappa et al, 2015).

The pre-questionnaire will consist of Attachments A, B, and C to establish a baseline. The postquestionnaire will consist of Attachments B, C, and D, also allowing the study to evaluate the response of subjects at high risk of OSA.

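### Dropping at-risk users who seek a sleep study or return the device, with two different survey triggers, leaves the secondary-objective rate open to loss or bias

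*Combined protocol and SAP*

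**What the plan says.** The opening section, Purpose and Background, sets the objective: "A secondary objective is to evaluate the behavior of patients at high risk for sleep apnea", specifically whether they will obtain a diagnosis through a sleep study.

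The section Obstructive Sleep Apnea (OSA) names three behaviors of at-risk users: seeking a study, returning the device for a refund, or using it. It says "This clinical trial will also monitor the behavior of these users", and then, of those who seek a study or return the device, "In the first two cases, they will be dropped from the clinical trial".

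The behavior is recorded in the follow-up survey. Under Study Design, users who identify themselves as at risk are surveyed as follows: "they will be asked about their response, including whether they sought medical care, enrolled in a sleep study", or stopped using the device. Under Data Collection, "The postquestionnaire will consist of Attachments B, C, and D". Attachment D is STOP-BANG. The baseline questionnaire is Attachments A, B and C, so it does not include STOP-BANG.

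The survey has two triggers:
- Study Design: "An email prompting them to complete a follow-up questionnaire will be sent ten days after the device has been received".
- Methods and Procedures: "After they have used the device for ten days, a follow-up survey will be emailed to the subject".

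Methods and Procedures also gives high-risk users the option to "discontinue use of the device and return it for a full refund", with no survey condition stated there. Costs to the Subject makes the refund of the purchase price depend on completing the follow-up.

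**The concern.** The drop rule applies to the very people who show the behavior that the secondary objective counts. If leaving the trial also means leaving data collection, the numerator (sought a study) is lost. So is part of the denominator, because STOP-BANG status is recorded only at follow-up.

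The second trigger adds to this. A user who returns the device early never completes ten days of use, so on the Methods and Procedures wording the survey is never sent. The same holds for a user who seeks a study and stops the device early.

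The resulting rate is the plan's evidence on the over-the-counter concern raised under Background, namely that a snoring device may keep people from a sleep study. A low recorded rate would appear to support the sponsor's stated theory that most such patients are not arranging studies anyway, even if it came only from who was surveyed.

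**Working it through.** **The plan's own figure.** The plan gives no target, denominator or precision for the secondary objective. Its only related number is enrolment: 350 / (1 − 0.30) = 500. That reproduces and is not in dispute. The 30% cannot serve as a non-response rate for users who continue, because Data Analysis and Monitoring includes discovery of moderate to severe sleep apnea in it.

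**The sections side by side.**

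| At-risk user | OSA section | Study Design trigger (receipt + 10 days) | Methods trigger (10 days of use) |
|---|---|---|---|
| Seeks a study | Dropped | Survey is sent | Sent only if use reaches ten days |
| Returns device early | Dropped | Survey is sent | Never sent |
| Continues | Kept | Survey is sent | Survey is sent |

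For users who start promptly and continue nightly, the two triggers nearly coincide. They part for those who stop or return the device.

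**Effect on the recorded rate.** The documents give no behavior or response rates, so all of these are assumptions. Let p be the share of high-risk users who seek a study, q the share who return the device, and 1 − p − q the share who continue. Let s, r and c be the fractions of seekers, returners and continuers who answer. Then

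recorded rate = s·p / (s·p + r·q + c·(1 − p − q)).

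With c = 1 throughout:

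| Who answers | p = 0.30, q = 0.20 (true 30%) | p = 0.10, q = 0.10 (true 10%) |
|---|---|---|
| No seekers | 0% | 0% |
| A quarter of seekers and returners | 0.075 / 0.625 = 12% | 0.025 / 0.85 = 2.9% |
| Half of seekers and returners | 0.15 / 0.75 = 20% | 0.05 / 0.90 = 5.6% |
| All seekers, no returners | 0.30 / 0.80 = 37.5% | 0.10 / 0.90 = 11.1% |
| Everyone | 30% | 10% |

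The first row is the literal drop rule. The fourth is the Methods trigger if seekers complete ten days of use and returners do not. The bias is downward when seekers are lost and upward when only returners are lost.

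**Precision with full capture.** As a rough assumption, take 10% to 22% of 500, that is 50 to 110 high-risk recipients, borrowing the shares of male and female snorers with OSA from the OSA section. This is a weak proxy: OSA prevalence is not the share screening high-risk on STOP-BANG, and 22% refers to women only while the Gender section expects more men. Wilson 95% intervals for a 30% rate are 19.1% to 43.8% (15/50) and 22.2% to 39.1% (33/110).

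**The case against.** The strongest reply is that the drop concerns efficacy only. The sentence before the drop rule says these users' behavior will be monitored. The survey items on sleep-study enrolment and discontinuation make sense only if such users are surveyed. Methods and Procedures repeats that responses are monitored, and Data Collection says the post-questionnaire serves this purpose. Counting apnea discovery in the 30% dropout fits a rule about who is among the roughly 350 completers. This has real force. A reader might infer that the plan discards its own secondary outcome and must record 0%; the documents do not say that. What stands is that nothing in the available text defines the drop or states that dropped users are surveyed, and the Methods trigger, read as written, misses early returners.

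It is also fair to say that the triggers differ by only days for most users. The problem is confined to those who stop, but they matter most for this objective.

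A reader might also see a contradiction in the refund terms. They can be two transactions: money back for returning the device, and money back for completing the survey. All that is missing is a statement of whether a returner's refund depends on the survey.

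Finally, the consent form and attachments are not available for review and may settle some of this.

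**Conclusion.** The point holds as an unresolved conflict that puts the secondary objective at risk, not as proof that its data will be lost. If the drop rule or the use-based trigger is followed literally, the sleep-study rate is 0% or biased in either direction. In the illustration with a true 30%, the recorded value runs from 0% to 37.5% depending only on who answers. Those figures rest on assumed behavior and response shares and on all continuers answering; only the 0% when no seekers are surveyed is independent of them.

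A reader might go on to infer that the efficacy result is biased. The documents do not support an estimate of that. They leave open only whether dropped users' responses enter the pre/post comparison, since neither Data Analysis and Monitoring nor Statistical Analysis says.

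Separately, the OSA section lists using the device as one of the at-risk user's choices. The three options in Methods and Procedures do not include continuing, although that section then plans to observe whether users continue. The sponsor must reconcile these passages.

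**What to change.** Reconcile the OSA section, Study Design, Methods and Procedures, and Data Collection so that leaving device use does not end data collection:

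1. Define what being dropped means, and state that dropped users are still surveyed.
2. Use one trigger: send the follow-up survey, with STOP-BANG and the response items, to every device recipient ten days after receipt, whatever their device use. Add an item on the number of nights used.
3. Log each device return with its date and reason, and state whether a returner's refund depends on the survey (Methods and Procedures; Costs to the Subject).
4. Report each response as a proportion of all identified high-risk recipients with a 95% CI, and give the number of recipients whose risk status is unknown.
5. State whether dropped users' responses enter the pre/post comparison, and report a sensitivity analysis with all available follow-up responses. Putting people who never used the device into the primary comparison would change its question, so that choice should be explicit.

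The cost is wording changes, a few more emails and a return log. Late starters will answer after slightly shorter exposure, which the nights-used item makes visible. The proportions will be imprecise, as the intervals above show.

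### High-risk subjects who seek a sleep study or return the device are dropped, with no statement that they stay in follow-up for the secondary objective, and the two survey triggers disagree

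*Combined protocol and SAP*

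**What the plan says.** All references are to the combined protocol and SAP.

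- **Objective.** Section II, Purpose and Background, sets a secondary objective for high-risk patients: to "determine whether they will seek a conclusive diagnosis with a sleep study".
- **Handling rule.** The Obstructive Sleep Apnea (OSA) section names three behaviours to watch: seeking a sleep study, returning the device for a refund, and using the device. It then adds: "In the first two cases, they will be dropped from the clinical trial".
- **Recording.** Study Design has the follow-up survey ask subjects who saw themselves as at risk "whether they sought medical care, enrolled in a sleep study, or discontinued use of the device". Data Collection places STOP-BANG (Attachment D) after treatment only: "The pre-questionnaire will consist of Attachments A, B, and C to establish a baseline", whereas "The postquestionnaire will consist of Attachments B, C, and D".
- **Survey timing.** Study Design: "An email prompting them to complete a follow-up questionnaire will be sent ten days after the device has been received". Methods and Procedures: "After they have used the device for ten days, a follow-up survey will be emailed to the subject".
- **Refund.** Among the options for high-risk subjects, Methods and Procedures lists "3) discontinue use of the device and return it for a full refund", with no survey condition stated. Under Costs to the Subject, other subjects recover the $90 only by completing the follow-up survey.
- **Dropout allowance.** Data Analysis and Monitoring counts discovery of moderate to severe apnea within the 30% dropout used to size the VAS comparison.

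**The concern.** The first behaviour that triggers removal is the secondary outcome itself. If a removed subject is not surveyed, the event that the objective is meant to count goes unrecorded. Because STOP-BANG is not in the pre-questionnaire, that subject's risk status goes unrecorded too, so the person is missing from both numerator and denominator.

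The survey trigger adds a second route of loss. Someone who stops or returns the device on day 3 still reaches ten days after receipt, but never reaches ten days of use.

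The Background section raises the worry that an OTC device may keep people from having a sleep study. The study-seeking proportion is the information this trial collects on that worry. If its denominator depends on who was dropped and who was emailed, the result is hard to interpret.

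**Working it through.** **1. The plan's own figure.** Data Analysis and Monitoring needs about 350 completers and allows 30% dropout: 350 / (1 − 0.30) = 500, as stated. The allowance is 500 − 350 = 150 subjects. It protects the number available for the VAS comparison. It does not provide for recording the secondary outcome in those who leave.

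**2. Who would be surveyed under each rule.** The entries follow from the wording of each section and assume that the trigger is applied as written.

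| High-risk subject | Study Design trigger (10 days from receipt) | Methods and Procedures trigger (10 days of use) | OSA section, read literally |
|---|---|---|---|
| Keeps using the device | surveyed | surveyed | stays in |
| Seeks a study, keeps using | surveyed | surveyed | dropped |
| Seeks a study, stops early | surveyed | not reached | dropped |
| Returns the device early | surveyed | not reached | dropped |

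Only the first row is treated alike throughout.

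**3. What is known without the survey.** A return has to be processed for a refund, so the sponsor would know that it happened. It would not know from this the returner's STOP-BANG result or whether a study was sought. STOP-BANG is also in the product instructions for self-administration, but the plan does not say that those answers are sent back.

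**4. Direction of the error.** Let *s*, *r* and *c* be the true shares of high-risk subjects who seek a study, return the device, and continue, treated as exclusive. Let *a* and *b* be the response rates of seekers and returners divided by that of continuing users.

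Observed seeking share = *s·a* / (*s·a* + *r·b* + *c*)

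The documents give none of these five values. All are assumed here, to show direction only.

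| Assumed response | *s, r, c* = 0.20, 0.20, 0.60 | *s, r, c* = 0.50, 0.20, 0.30 |
|---|---|---|
| All answer equally (*a* = *b* = 1) | 0.20/1.00 = 20.0% (true) | 0.50/1.00 = 50.0% (true) |
| No seeker answers (*a* = 0) | 0% | 0% |
| Both answer half as often (*a* = *b* = 0.5) | 0.10/0.80 = 12.5% | 0.25/0.65 = 38.5% |
| Seekers answer equally, no returner does (*a* = 1, *b* = 0) | 0.20/0.80 = 25.0% | 0.50/0.80 = 62.5% |
| Losses cancel (*b* = 0; *a* = 0.75 and 0.60 respectively) | 0.15/0.75 = 20.0% | 0.30/0.60 = 50.0% |

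The share is understated when seekers are lost and overstated when mainly returners are lost. It can also come out right by chance. The refund terms make the overstated case plausible: seekers who keep the device need the survey to recover $90, while returners are offered a refund with no stated survey condition.

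**The case against.** The strongest reply is that *dropped* means only left out of the efficacy completers. Much supports it. The OSA section says that these behaviours will be monitored, and a subject can be dropped for a behaviour only once it is known. Methods and Procedures repeats the intention to monitor. Study Design asks about sleep-study enrolment and discontinuation, which would be pointless if such subjects were never surveyed. Data Collection says that the post-questionnaire serves to evaluate the high-risk response. The dropout allowance treats apnea discovery as a loss to the VAS comparison. I accept this as the likelier intent. No section states it, however, and none says that dropped subjects stay in follow-up or in the secondary denominator.

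It can also be said that the trigger conflict is loose wording. No tracking of nights used is described, so time from receipt is the trigger that the procedures can operate, and for a fully compliant subject the two may coincide. That is fair, but they part for the early stoppers and returners, who matter here.

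Two stronger readings are tempting. A reader might infer that the survey is the sole record of the behaviour. The plan supports only that it is the sole instrument named; returns would show in refund processing, and the attachments are not in the text available. A reader might also infer that the seeking proportion must come out near zero or too low. Nothing says that seekers go unsurveyed, and those who keep the device have a $90 reason to answer.

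Finally, a single-arm proportion over about ten days cannot show whether the device deters people from sleep studies, even with perfect capture. That limits what the result can prove, but it does not excuse losing subjects because of their outcome.

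**Conclusion.** The point holds as an unresolved conflict in the plan. Followed literally, the drop rule and the trigger based on use remove subjects selected by the secondary outcome, and enrolling more people does not cure that. On the likelier reading of *dropped*, the trigger based on use still misses early stoppers and returners.

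Neither the size nor the direction of any bias can be derived: the documents give no high-risk share, no split of behaviours and no response rates. The percentages above illustrate direction and are not estimates. The documents do not support a claim that the outcome will go unrecorded, or that the bias has a known sign.

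This is minor to moderate and concerns the secondary objective only, for which the plan states no test, threshold or sample size. The conclusion rests on the text as available, without the attachments.

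**What to change.** 1. In the Obstructive Sleep Apnea (OSA) section, state that study seekers and device returners leave only the VAS/SSS efficacy set and stay in data collection for the secondary objective.
2. In Methods and Procedures, adopt the Study Design trigger: send the survey to every enrolled subject ten days after receipt, whether or not the device is still in use. Add one item on nights used, so that the efficacy set can still be defined.
3. Record study sought, device returned and continued use as three separate yes/no items, since one person can do more than one.
4. Report the seeking proportion among high-risk responders, with the numbers surveyed and responding.

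Optional extras are STOP-BANG and response items on a device-return form, and a comparison of responders with non-responders on baseline age, gender, BMI and SSS.

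**Cost.** Two short rewordings, a few survey items and a few more surveys to process. Enrolment stays at 500, and the 30% allowance already covers these subjects leaving the efficacy set. There are two downsides. Late starters will have fewer than ten nights of use when surveyed. High-risk non-responders stay uncounted, because STOP-BANG is not collected at baseline.
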